4. STUDY POPULATION

4.1 Population

- Recipients of alloSCT (age 0-75 years) with CMV reactivation who fail antiviral therapy (defined as **CMV reactivation treatment failure**: persistent CMV DNA load of more than 1000 cp/ml or CMV disease after 2 weeks of adequate treatment with antiviral therapy or relapse of CMV DNA load of more than 1000 cp/ml within 4 weeks after adequate treatment with antiviral therapy or contraindication for treatment with antiviral therapy at the discretion of the physician) **or**
- Patients who develop **CMV disease** (organ dysfunction (pneumonitis, enteritis, retinitis, encephalitis, hepatitis, and bone marrow suppression) due to CMV infection).
- Number of patients to be treated with CMV pp 65 specific T cells will be 15.

4.2 Inclusion criteria

- age 0-75 years
- recipient of alloSCT for standard indication according to national- and European Group for blood and Marrow Transplantation-guidelines (see appendix D)
- Possibility to obtain PBMC by leukapheresis from the CMV seropositive donor or availability of peripheral blood stem cell graft (PBSCT) or of a CD34-negative subfraction of a CD34-positively selected PBSCT product of the donor prepared and cryopreserved at a GMP-facility or stem cell center.
- **CMV reactivation treatment failure** (persistent CMV DNA load of more than 1000 cp/ml or CMV disease after 2 weeks of adequate treatment with antiviral therapy or relapse of CMV DNA load of more than 1000 cp/ml within 4 weeks after adequate treatment with antiviral therapy or contraindication for treatment with antiviral therapy at the discretion of the physician) **or** **CMV disease** (organ dysfunction (pneumonitis, enteritis, retinitis, encephalitis, hepatitis, and bone marrow suppression) due to CMV infection).
- Written informed consent by the patient and/or parent(s) or legal guardian(s).

4.3 Exclusion criteria

- Life expectation < 3 months.
- End stage irreversible multi-system organ failure.
- Pregnant or lactating women.
- Severe psychological disturbances.
- Patient HIV positive.
- Donor HIV positive.

4.4 Sample size calculation

We consider the infusion of CMV pp65-specific T cells a success when the response rate is at least 66 % (p_1 ; 2/3 of patients). Based on our historical experience, we

estimate the rate of responses with pharmacotherapy alone but without immune intervention to be 30% ($=p_0$) for the targeted patient population. Given the high laboratory effort and associated costs of treatment with CMV pp65-specific T cells, the trial should have a power of 90% (beta-error 0.1). With the usual alpha-error of 0.05, the sample size as calculated according to the standard Fleming design is 15 treated patients under these assumptions. On the basis of the currently performed phase I/II clinical study (LUMC 2004-01) on the treatment of refractory CMV reactivation we expect to include 5-7 patients per year for a period of 3 years. We expect no excess in number of events of acute GvHD, death and all other adverse events.

5. TREATMENT OF SUBJECTS

5.1 Investigational product

The CMV pp65-specific T cell product will be generated from PBMC from a leukapheresis product, from a peripheral blood stem cell graft (PBSCT material) or from a CD34-negative subfraction of a CD34 positively selected stem cell graft from a CMV seropositive donor prepared and cryopreserved at a GMP-facility or stem cell center, whichever is available.

PBMC will be exposed to the CMV pp65-derived 15 mer peptide pool, after which CMV-pp65-specific T cells will start to produce Interferon gamma (IFN γ). After overnight incubation, IFN γ secreting T cells will be isolated using the CliniMACS® Cytokine Capture System. The positively isolated fraction will be washed, after which the percentage of IFN γ - and CD137-positive T cells will be determined. When $\geq 20\%$ of the T cells are IFN γ and/or CD137 positive the CMV pp65 T cell product will be released. The number of cells that will be infused in the patient will be determined by the number of non-specific T cells in the product. The maximal amount of non-specific T cells in the product is $< 0.3 \times 10^6/\text{kg}$ body weight in patients transplanted with related donors and $< 0.15 \times 10^6/\text{kg}$ body weight in case of unrelated donors, the CMV pp65 T cell product will be released for administration.

After release, the CMV-pp65-specific T cell product will be resuspended in a solution of NaCl 0,9%, supplemented with human albumin (2%), after which the product can be administered.

5.2 Investigational treatment

CMV pp65-specific T cells are a cell therapy product that will be administered after alloSCT in case of CMV reactivation treatment failure or CMV disease. The CMV pp65-specific T cells will be generated from a CMV seropositive donor. The product will contain an aimed dose of $10\text{-}20 \times 10^6$ total T cells. This dose is based on the amount of cells we expect to isolate on the basis of the currently performed phase I/II clinical study (LUMC 2004-01) on the treatment of refractory CMV reactivation using CMV pp65-specific CD8+ T cells and preclinical data of the current strategy. All cells isolated will be infused if $\geq 20\%$ of the T cells are IFN γ and/or CD137 positive and the maximal amount of non-specific T cells in the product is $< 0.3 \times 10^6/\text{kg}$ body weight in patients transplanted with related donors and $< 0.15 \times 10^6/\text{kg}$ body weight in case of unrelated donors. If the number of non-specific T cells in the product exceeds these criteria, the infused dose will be adjusted accordingly. The cells will be administered intravenously at the department of Hematology of the LUMC. In case of ongoing CMV reactivation or CMV disease and no severe toxicity, the procedure may be repeated 2 times with at least 4 weeks interval.

5.3 Collection of donor PBMC

Donor PBMC will be collected by leukapheresis using acid citrate dextrose-anticoagulant (ACD-A) as anticoagulant. The leukapheresis procedure per

mononuclear cell dose will be restricted to maximally 6 hours per session and maximally 12 hours in total with a maximal volume of blood to be processed of 20 liters per session with an aimed number of 1×10^8 PBMC/kg body weight. Donor PBMC that are not used for generation of CMV pp65-specific T cells will be cryopreserved for future usage as unselected DLI.

5.4 Contraindications for administration of CMV pp65-specific T cells

- Life expectation < 6 weeks.
- End stage irreversible multi-system organ failure.
- Acute GvHD overall grade \geq III.
- Treatment with corticosteroids in an equivalent dose of >0.5 mg/kg prednisone.
- No CMV reactivation or CMV disease.

5.5 Use of co-intervention

Antiviral therapy will be continued after infusion of CMV pp65-specific T cells according to standard antiviral treatment protocols at the discretion of the physician.

5.6 Escape medication

Patients will receive routine clinical care for alloSCT patients. All medication and other treatments administered will be noted and continued if considered necessary by the treating physician.

5.7 Escape administration of cultured CMV pp65-specific T cell line

If after generation of the CMV pp65-specific T cells by peptide stimulation and IFN γ isolation the release criteria for direct administration of the cells are not met, the patient will go off protocol. When between 5 – 20% of the isolated T cells are IFN γ positive the T cell product will be cultured in vitro to enrich for the specific T cells. If After 7 – 10 days of culture the CMV pp65-specific T cell line meets the release criteria, the cells will be administered to the patient if clinically indicated.

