2. OBJECTIVES

- To assess the feasibility, tolerability and safety of administration of donor derived CMV pp65-specific T cells in patients with CMV reactivation or CMV disease after alloSCT.
- To determine the presence of CMV-specific T cells at different time points after infusion of CMV pp65-specific T cells.
- To evaluate whether administration of CMV pp65-specific T cells in patients with persistent CMV reactivation or CMV disease after alloSCT leads to complete or partial responses.

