6.3 Summary of findings from clinical studies

Since the introduction of protocol LUMC 2004-01 for the treatment of therapy-resistant CMV reactivation or disease after alloSCT, twelve donor-derived CMV-specific CD8+ T cell lines have been generated. Of those cell lines, eight have been infused in six patients with no side effects. All treated patients cleared the CMV within weeks after infusion.

For a more extensive overview of the clinical studies on CMV-specific T cells, please refer to the IMPD.

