9.2 Planned sample size

We aim to include 15 patients. On the basis of the currently performed phase I/II clinical study (LUMC 2004-01) on the treatment of refractory CMV reactivation we expect to include 5-7 patients per year for a period of 3 years.

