9.3 Power calculation

We consider the infusion of CMV pp65-specific T cells a success when the response rate is at least 66 % (p_1 ; 2/3 of patients). Based on our historical experience, we estimate the rate of responses with pharmacotherapy alone but without immune intervention to be 30% ($=p_0$) for the targeted patient population. Given the high laboratory effort and associated costs of treatment with CMV pp65-specific T cells, the trial should have a power of 90% (beta-error 0.1). With the usual alfa-error of 0.05, the sample size as calculated according to the standard Fleming design is 15 treated patients under these assumptions. We expect no excess in number of events of acute GvHD, death and all other adverse events.

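### The feasibility part of objective 1 has no endpoint, release failures leave the protocol, and response is counted only in infused patients

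*Protocol*

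**What the plan says.** The first objective (Protocol, Section 2) is "To assess the feasibility, tolerability and safety of administration of donor derived CMV pp65-specific T cells". Sections 3 and 9.1 both call the trial a phase I/II feasibility study.

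Section 7.1 lists three endpoints: adverse events including acute GvHD and death; CMV-specific T-cell numbers after infusion; and complete or partial responses after infusion. Section 9.4 analyses these and nothing else that bears on feasibility.

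The release rule in Section 5.1 is that when at least 20% "of the T cells are IFN γ and/or CD137 positive the CMV pp65 T cell product will be released". Too many non-specific T cells is handled differently in Section 5.2: "If the number of non-specific T cells in the product exceeds these criteria, the infused dose will be adjusted accordingly". Section 5.7 says that if "the release criteria for direct administration of the cells are not met, the patient will go off protocol". It then describes a culture route: "When between 5 – 20% of the isolated T cells are IFN γ positive the T cell product will be cultured in vitro", and the cultured cells may be given later if they meet release.

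Section 9.3 sets a 66% target against 30% for pharmacotherapy alone in the target population, and says the sample size "is 15 treated patients under these assumptions". Section 9.2 says "We aim to include 15 patients".

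**The concern.** A feasibility study of a new manufacturing route should say how often the route works. The product here is new: a peptide pool, overnight selection, direct infusion without culture, a purity threshold and a dose that is only aimed at. Nothing in the protocol counts starts, releases or infusions as an outcome. Section 5.7 also removes the patients in whom the route failed, and follow-up in Section 3 runs from infusion, so no outcome follow-up is specified for them.

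The second consequence concerns efficacy. The observed response rate describes patients who had a releasable product and were infused. The 30% describes everyone in the target population. With no denominator of all patients started, a reader of the final report could not tell how much of the difference comes from the cells and how much from selection, nor what a patient entering the pathway can expect.

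**Working it through.** **Step 1: reproduce the sample size.** Inputs from Section 9.3: p0 = 0.30, p1 = 0.66, alpha 0.05, power 0.90. The sidedness is not stated; one-sided is assumed here.

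n = [(z_alpha × √(p0(1−p0)) + z_power × √(p1(1−p1))) / (p1 − p0)]²
= [(1.645 × √0.21 + 1.282 × √0.2244) / 0.36]² = 14.29, rounded up to 15.

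The stated 15 reproduces. As an exact check, 8 or more responses in 15 gives alpha 0.05001 and power 0.902. The problem is the denominator, not the arithmetic.

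**Step 2: set the objective beside the endpoints.**

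| Part of objective 1 | Endpoint in 7.1 | Analysis in 9.4 |
|---|---|---|
| Safety, tolerability | Adverse events, acute GvHD, death | Tabulated toxicity; causes of death |
| Feasibility | None | None |

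**Step 3: identify who is lost.** Under Section 5.2, excess non-specific cells lead to dose adjustment. Failing release therefore mainly means missing the 20% threshold. Those patients go off protocol under Section 5.7.

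**Step 4: size the denominator effect.** Let f be the share of started patients whose product fails release. The protocol does not give f, so 10% to 50% is an assumption.

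- Starts needed for 15 treated = 15 / (1 − f), rounded up.
- Rate among all started, failures as non-responders = (1 − f) × 0.66.
- Rate among all started, failures responding at the protocol's 30% = (1 − f) × 0.66 + f × 0.30.

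| f | Starts | Failures as non-responders | Failures at 30% |
|---|---|---|---|
| 10% | 17 | 59.4% | 62.4% |
| 20% | 19 | 52.8% | 58.8% |
| 25% | 20 | 49.5% | 57.0% |
| 40% | 25 | 39.6% | 51.6% |
| 50% | 30 | 33.0% | 48.0% |

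**Step 5: what a report would show.** Take f = 25%, 10 responders and no response among failures. Release and infusion succeed in 15/20 = 75% (exact 95% CI 51% to 91%). Response is 10/15 = 67% (38% to 88%) per infused patient and 10/20 = 50% (27% to 73%) per started patient. As written, the protocol calls only for the 10/15.

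**The case against.** Several counter-arguments have force.

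- **The first objective is not unanswerable.** A reader might infer that the trial cannot meet it at all. The first endpoint has no after-infusion limit and covers safety and tolerability. Infused doses are documented (Section 7.2.2), eligibility is verified at inclusion (Section 11.1), and the annual report gives numbers included and completed (Section 11.2). Feasibility could probably be pieced together afterwards. What stands is that it is not prespecified, and that none of these records requires release success or the reason for failure.
- **A rate per infused patient fits objective 3**, which asks about the effect of administration, and treated patients are the declared sample-size unit. This stands, and that rate should stay primary.
- **Selection need not be favourable.** Release depends on donor cells and selection is overnight, so failure need not track the patient's prognosis. The documents do not settle the direction.
- **Intervals and supportive analyses are normal SAP content.** True, but the endpoints and the rule on who leaves the study are fixed in the protocol.
- **The earlier study gives no failure rate.** A reader might take one from Section 6.3, which reports twelve donor-derived lines: "Of those cell lines, eight have been infused in six patients with no side effects" (Section 1 says sixteen lines). The reasons for non-infusion are not given, lines are not patients, and that product was HLA-restricted, CD8-only and cultured.
- **Loss of power does not follow.** A reader might infer it from Section 9.2. But the Summary and Sections 4.1, 4.4 and 9.3 all say 15 treated, and the end of study is tied to the infusion of patient 15 (Section 7.6). Power at smaller numbers also depends heavily on the cut-off: with 15 patients, holding strictly to 5% requires 9 responses and gives power 0.78, against 0.90 with 8.
- **Contraindications in Section 5.4 are not a removal rule.** They are checked before infusion, and some are not exclusion criteria in Section 4.3, so an included patient may go uninfused. The protocol neither withdraws such patients nor bars later infusion.

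**Conclusion.** The point holds in a limited form and should be corrected. Feasibility is an objective without a measure, and Section 5.7 takes out of the trial the patients who would inform it. The response rate is conditional on release and infusion, while its benchmark is not.

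The size depends on a failure rate that the protocol does not state. Across an assumed 10% to 50%, a 66% rate among treated patients is 59% to 33% of all started with failures as non-responders, or 62% to 48% with failures responding at 30%. If few products fail, the gap is small; the trial as planned would not report which case applies.

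The sample size of 15 treated is sound on a one-sided normal approximation. The 15 included in Section 9.2 is a wording conflict, not evidence that power is lost.

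**What to change.** 1. **Sections 7.1 and 9.4:** add a feasibility endpoint: patients infused with a released product divided by all patients for whom donor-cell selection was started, with an exact 95% confidence interval and the reason for each non-infusion.
2. **Section 5.7:** state that a patient without a released product receives no study infusion under this protocol but stays in data follow-up from routine records for CMV outcome, GvHD and survival. Any off-protocol cultured cells are recorded and reported separately. Clinical management is unchanged.
3. **Section 9.4:** report response per infused patient (primary, against 30%) and per started patient (supportive).
4. **Section 9.2:** reconcile the 15 included with the 15 treated in Sections 4.1 and 9.3.

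The cost is an amendment and light data collection on what may be only a few non-infused patients; it grows with the failure rate and with any recording of cultured-cell treatment. The rate per started patient will probably look less favourable than the rate per infused patient.

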6. INVESTIGATIONAL MEDICINAL PRODUCT

6.1 Name and description of Investigational Medicinal Product

CMV pp65-specific T cells are a cell therapy product. This particular product consists of a T cell suspension which is generated from PBMC, PBSCT material or CD34 negative cell fraction from a donor (allogeneic T cell product). CMV pp65-specific T cells are isolated from the starting material under Good Manufacturing Practice (GMP) conditions following Standard Operating Procedures (SOPs) of the Interdivisional GMP Facility LUMC (IGFL) and the Department of Hematology. Technical details regarding CMV pp65-specific T cells and the production process are presented in the Investigational Medicinal Product Dossier (IMPD).

6.2 Summary of findings from non-clinical studies

CMV pp65-specific CD8+ and CD4+ T cells are circulating within the peripheral blood of CMV infected individuals for the control of CMV. CMV-specific T cells can be isolated from PBMC. We have demonstrated that stimulation of PBMC from CMV infected individuals with the CMV pp65 protein-spanning 15-mer (11 mer overlapping) peptide pool induced simultaneous activation of both CMV pp65-specific CD8+ and CD4+ T cells, irrespective of the HLA type. Activated CMV-specific CD8+ and CD4+ T cells both produce IFN γ and CMV pp65-specific T cells can be isolated from PBMC based on their IFN γ production using the cytokine capture system from Miltenyi Biotec. Isolation of IFN γ -secreting cells after stimulation with the CMV pp65 15 mer peptide pool resulted in efficient enrichment of CMV-specific CD8+ and CD4+ T cells recognizing multiple CMV pp65-derived epitopes. Isolated CMV pp65-specific CD4+ and CD8+ T cells retain their functionality and can be activated upon antigenic stimulation.

For a more extensive overview of preclinical data on CMV-specific T cells, please refer to the IMPD.

6.3 Summary of findings from clinical studies

Since the introduction of protocol LUMC 2004-01 for the treatment of therapy-resistant CMV reactivation or disease after alloSCT, twelve donor-derived CMV-specific CD8+ T cell lines have been generated. Of those cell lines, eight have been infused in six patients with no side effects. All treated patients cleared the CMV within weeks after infusion.

For a more extensive overview of the clinical studies on CMV-specific T cells, please refer to the IMPD.

6.4 Summary of known and potential risks and benefits

Risks:

The CMV pp65-specific T cell product is released when 20% of the T cells is specific for CMV pp65, indicating that 80% of the cells might be not specific for CMV pp65.

The consequence of this approach is that no exact information is obtained concerning the reactivity of IFN γ - and CD137-negative T cells in the CMV pp65-specific T cell product. To minimize the risk of GvHD to a minimum, the amount of IFN γ /CD137 negative T cells administered in the T cell product will be $< 0.3 \times 10^6$ /kg body weight in case of a related donor and $< 0.15 \times 10^6$ /kg body weight in case of an unrelated donor.

CMV pp65-specific T cells will be generated for the treatment of CMV reactivation or CMV disease in patients after alloSCT. To increase the potential clinical use of CMV-specific T cells and to increase the in vivo potential of the CMV-specific T cells CMV pp65-specific T cell lines will be generated using CMV pp65 peptide pool, which is not restricted to certain HLA-types and will induce CD4+ and CD8+ T cell responses. Furthermore, the CMV pp65-specific T cells will be isolated after one day of culture and will be directly administered after isolation. In this way we can shorten the period between the onset of refractory CMV reactivation/CMV disease and the infusion of the CMV-specific cells and furthermore we expect that the in vivo potential of the T cells will be increased. For more information on the overall risk and benefit assessment, please refer to the IMPD.

6.5 Description and justification of route of administration and dosage

The CMV pp65-specific T cells will be administered intravenously. The aimed dose of CMV pp65-specific T cells of $10\text{-}20 \times 10^6$ total T cells is based on the amount of cells we expect to isolate on the basis of the currently performed phase I/II clinical study (LUMC 2004-01) on the treatment of refractory CMV reactivation using CMV pp65-specific CD8+ T cells and preclinical data of the current strategy. All cells isolated will be infused to maximize the effect if $\geq 20\%$ of the T cells are IFN γ and/or CD137 positive and the maximal amount of non-specific T cells in the product is $< 0.3 \times 10^6$ /kg body weight in patients transplanted with related donors and $< 0.15 \times 10^6$ /kg body weight in case of unrelated donors. The maximal amount of non-specific T cells administered in the T cell product is based on the current protocol for unselected DLI at 3 months in which comparable numbers of unselected CD3 positive cells are administered with acceptable toxicity. If the number of number of non-specific T cells in the product exceeds these criteria, the infused dose will be adjusted accordingly.

6.6 Dosages, dosage modifications and method of administration

The CMV pp65-specific T cells will be infused intravenously over 30 minutes via a peripheral intravenous access, or, if already in place, an in-situ venous access device.

The aimed dose of CMV pp65-specific T cells is $10\text{-}20 \times 10^6$ total T cells, with $>20\%$ IFN γ secreting T cells and containing $< 0.3 \times 10^6$ /kg body weight T-cells with unknown specificity in case a patient was transplanted with an HLA-matched sibling and $< 0.15 \times 10^6$ /kg body weight T-cells with unknown specificity in case a patient was transplanted with an HLA-matched unrelated donor.

